### 13.3 Primary Safety Endpoint Statistical Plan

Safety and tolerability for abemaciclib monotherapy and for the combination of abemaciclib and atezolizumab will be summarized by rate of dose-limiting toxicities (DLTs) as defined in section 7.3 using percentage and 90% confidence interval, and by incidence and grade of adverse events (AEs) by CTCAE version 5.0. Safety analyses will be performed for all patients who have received at least one dose of study drug.

Bayesian toxicity monitoring (<https://trialdesign.org/one-page-shell.html#BTOX>) was planned to be used for all patients enrolled to Arm B and to the combination treatment cohort of Arm C (up to a maximum of 43 patients) starting after three patients have initiated treatment. If the rate of patients experiencing dose limiting toxicities (DLTs) at the starting dose exceeded the pre-specified threshold for excessive toxicity, then subsequent patients randomized to Arm B or enrolled to the combination cohort of Arm C were planned to de-escalate abemaciclib dose to 100 mg BID with atezolizumab 1200 mg every 21 days with Bayesian toxicity monitoring resuming once three additional patients have initiated treatment at this lower dose level. If the rate of patients experiencing DLT at the de-escalated dose exceeded the pre-specified threshold for excessive toxicity, then enrollment to Arm B and the combination cohort of Arm C were planned to be halted. Maximum probability of DLT is 0.3 with prior distribution of  $B(0.5, 0.5)$  for the DLT rate. Stopping probability threshold for excessive DLT is 0.7. Dose de-escalation or early stopping of enrollment for combination cohort will follow the rules displayed in Table 28.

**Table 28.** Decision rules for dose de-escalation or early stopping

# DLT-evaluable  patients treated at current dose level	3	4	5	6	7	8	9	10	11	12	13	14	15	16	17	18	19	20	21	22	
Reduce dose or stop early if # pts experiencing DLT is >	2	2	2	3	3	4	4	4	5	5	5	6	6	6	7	7	7	8	8	8	
# DLT-evaluable  patients treated at current dose level	23	24	25	26	27	28	29	30	31	32	33	34	35	36	37	38	39	40	41	42	43
Reduce dose or stop early if # of pts experiencing DLT is >	9	9	9	9	10	10	10	11	11	11	12	12	12	13	13	13	14	14	14	15	15

Patients must have received at least 28 days of trial therapy (or have experienced a DLT) to be considered DLT-evaluable.

**Table 29.** Operating characteristics under 5 scenarios of true DLT rates

Scenario	Probability of true DLT	Probability of dose de-escalation or early stopping	Probability of declaring DLT	Average # patients	Average # pts w/ DLTs	Observed DLT rate
1	0.1	0.09	0.09	39.6	4.0	0.13
2	0.2	0.34	0.34	30.6	6.1	0.29
3	0.3	0.71	0.71	18.7	5.6	0.43
4	0.4	0.94	0.95	9.6	3.9	0.52
5	0.5	1.00	1.00	5.6	2.8	0.59

Due to two grade 5 sepsis events observed in the 8 patients treated on Arm B with unclear relationship to the study medications, the Sponsor-Investigator and co-investigators elected to halt enrollment to combination treatment rather than following the Bayesian toxicity monitoring plan. Unselected patients will continue to enroll on Arm A in a non-randomized fashion (up to 27 patients in total in Arm A) and patients with CDK12 loss subsequently enrolled on Arm C after the 5 patients treated with atezolizumab monotherapy will receive abemaciclib 200 mg BID as monotherapy (total enrollment on Arm C up to 21 patients in total).

### 13.4 Secondary Endpoint Analysis Plan

Clinical benefit rate estimated by proportion of evaluable patients who had complete response (CR), partial response (PR) or stable disease (SD) as their best response to treatment will be reported by treatment arm with 95% binomial confidence intervals. Overall survival (OS) among all patients, and among responders, duration of response (DOR), duration of therapy (DOT), and time to progression (TTP) will each be reported by treatment arm using Kaplan-Meier methods. Safety endpoints including the number and severity of adverse events will be summarized for each treatment arm using counts and proportions.

### **13.5 Statistical Plan for Primary Exploratory Endpoint Requiring Biopsies**

The primary biomarker study from the mandatory on-treatment biopsy for unselected mCRPC will be FoxP3+/CD8+ T-cell ratio. We expect the ratio of FoxP3+/CD8+ T-cells in archival pre-treatment tissue to be ~10% (96). We expect this ratio to decrease to ~5% with abemaciclib monotherapy. With 27 patients in arm A, we expect 22 samples in each arm to be evaluable for this endpoint. The FoxP3+/CD8+\_T-cell ratio in all biopsy specimens and the change between pre-treatment and on-treatment specimens will be reported descriptively in each treatment arm separately. The study will have at least 80% power at a 0.05 significance level to detect an effect size of 0.90 in change in FoxP3+/CD8+ T-cells ratio means between the combination group and the monotherapy group, using a two-sided Mann-Whitney test.

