Number of Subjects	Arms A and B: 35 total (27 in Arm A and 8 in Arm B) Arm C: 21 total Total trial: 56 patients
Inclusion Criteria	(All patients) 

1 Diagnosis of metastatic castration resistant prostate cancer (mCRPC), with histologic confirmation of adenocarcinoma of the prostate, without evidence of small cell carcinoma.

2 Adult males 18 years of age or older.

3 ECOG performance status of 0 or 1.

4 Presence of a lesion (bone or soft tissue) amenable to image-guided percutaneous biopsy, and patient evaluable for response based on: baseline PSA <math>\geq</math> 2 ng/mL OR measurable disease per RECIST 1.1 criteria.

5 Past progression or intolerance to at least one novel antiandrogen therapy (abiraterone, enzalutamide, galeterone, apalutamide, darolutamide, orteronel, seviteronel or equivalent) in either the hormone-sensitive or castration-resistant disease setting.

6 Not a candidate for docetaxel or cabazitaxel chemotherapy due to:

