## **9.4 Analysis Plan for Correlative Studies**

### **9.4.1 Immune infiltrate from tumor biopsies**

An exploratory endpoint for this study is FoxP3+/CD8+ ratio paired differences between pre-treatment archival tissue and on-treatment biopsies. These paired differences will be compared between the unselected monotherapy group and the combination therapy group. We estimate that 15 patients will have evaluable pre-treatment and on-treatment biopsies per treatment group. In this case, the study will have at least 80% power to detect an effect size of 1.1 using a two-sided Mann-Whitney test at a 0.05 significance level. We are confident that both these effect size estimates are attainable and are clinically meaningful in this study population.

We will also explore correlation of immune infiltrate with genetic features as described below.

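### Sections 9.4.1 and 13.5 still claim 80% power for a combination-versus-monotherapy biomarker test, but with Arm B closed at 8 patients the power is about 40–65%

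*Combined protocol and SAP*

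**What the plan says.** Section 13.5 covers the FoxP3+/CD8+ T-cell ratio from the mandatory on-treatment biopsies. It makes three statements that bear on this point:

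- On sample size: "With 27 patients in arm A, we expect 22 samples in each arm to be evaluable for this endpoint".
- On analysis: the ratio and its change from pre-treatment "will be reported descriptively in each treatment arm separately".
- On power: "The study will have at least 80% power at a 0.05 significance level to detect an effect size of 0.90" in the change in the ratio "between the combination group and the monotherapy group, using a two-sided Mann-Whitney test".

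Section 9.4.1 describes the same biomarker differently. On analysis: "These paired differences will be compared between the unselected monotherapy group and the combination therapy group". On sample size: "We estimate that 15 patients will have evaluable pre-treatment and on-treatment biopsies per treatment group". It then gives at least 80% power for an effect size of 1.1 with a two-sided Mann-Whitney test at the 0.05 level.

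The Synopsis gives the enrolment as "Arms A and B: 35 total (27 in Arm A and 8 in Arm B". Sections 1.1 and 13.3 say that enrolment to combination treatment has been halted. Arm C now consists of 5 patients on atezolizumab alone and 16 on abemaciclib alone.

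**The concern.** Only Arm B patients receive the combination, and there are 8 of them. The 22 or 15 combination samples on which the two power statements rest therefore cannot be obtained. Both statements describe a design with equal arms, and that design has ended.

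The text also gives two answers on what will be done. Section 9.4.1 plans a between-group test. Section 13.5 plans description by arm, then quotes the power of a between-group test in its next sentence. An analyst following one section would run a comparison that an analyst following the other would not.

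If the test is run, a non-significant result from at most 8 combination patients would stand beside a stated power of 80%. It could then be read as evidence that adding atezolizumab does not change the immune infiltrate. In addition, patients who entered Arm A after Arm B closed were not randomized, so the comparison is no longer a fully randomized one.

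**Working it through.** **Inputs from the documents**

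- Section 13.5: effect size 0.90, two-sided α = 0.05, 22 evaluable per arm.
- Section 9.4.1: effect size 1.1, two-sided α = 0.05, 15 evaluable pairs per group.
- Synopsis: 27 patients in Arm A, 8 in Arm B.

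**Assumptions.** The documents give no standard deviation, so effect size is read as a standardized mean difference d with normal data. They give no evaluable count for Arm B. The range used runs from all 8 down to the plan's own evaluable shares: 8 × 22/27 = 6.5 (so 6 or 7) and 8 × 15/27 = 4.4 (so 4 or 5).

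**Method.** Power of the two-sample t test, with each group size multiplied by the asymptotic relative efficiency of the Mann-Whitney test for normal data, 3/π = 0.955:

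δ = d × √(0.955 × n₁n₂/(n₁ + n₂)), with df = 0.955 × (n₁ + n₂) − 2

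Power is the probability that a noncentral t variable with noncentrality δ exceeds the two-sided 5% critical value in absolute size. As a check, the exact Mann-Whitney test was simulated on 20,000 normal data sets per case.

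**Step 1: reproduce the plan's figures**

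- 22 versus 22, d = 0.90: δ = 0.90 × √(0.955 × 11) = 2.92. Power is 0.812 by formula and 0.818 by simulation.
- 15 versus 15, d = 1.1: δ = 1.1 × √(0.955 × 7.5) = 2.94. Power is 0.810 by formula and 0.796 by simulation.

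Both statements are right for equal groups.

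**Step 2: put in the actual Arm B**

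| Arm A | Arm B | d | δ | Formula | Simulation |
|---|---|---|---|---|---|
| 22 | 8 | 0.90 | 2.13 | 0.537 | 0.505 |
| 22 | 7 | 0.90 | 2.03 | 0.496 | 0.486 |
| 22 | 6 | 0.90 | 1.91 | 0.450 | 0.419 |
| 15 | 8 | 1.1 | 2.46 | 0.647 | 0.633 |
| 15 | 5 | 1.1 | 2.08 | 0.502 | 0.450 |
| 15 | 4 | 1.1 | 1.91 | 0.435 | 0.413 |

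For example, 22 versus 8 gives n₁n₂/(n₁ + n₂) = 176/30 = 5.87, so δ = 0.90 × √(0.955 × 5.87) = 2.13.

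**Step 3: can more Arm A samples rescue it?**

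- All 27 Arm A and all 8 Arm B patients evaluable, d = 0.90: 0.563 by formula, 0.541 by simulation.
- Unlimited Arm A samples against 8, d = 0.90, normal approximation: δ = 0.90 × √(0.955 × 8) = 2.49, and 2.49 − 1.96 = 0.53, which gives power of about 0.70.
- The 22-sample count paired with the larger effect size, 22 versus 8 at d = 1.1: 0.708 by formula, 0.687 by simulation. Neither section states this combination.

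**Step 4: effect detectable with 80% power**

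By formula, about 1.23 SD for 22 versus 8 and 1.37 SD for 22 versus 6. Simulation gives 1.25 and 1.45. For the 9.4.1 count, the formula gives 1.32 SD for 15 versus 8 and 1.72 SD for 15 versus 4.

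**Step 5: sensitivity to normality**

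Replacing 3/π with values from 0.864 (the lower bound) to π²/9 (logistic data) moves the step 2 range to about 0.40–0.71. All of it is below 0.80.

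**The case against.** The strongest reply is that nothing was miscalculated. Both figures are correct for the design they were written for, and what remains is text that was not updated when Arm B closed. In 13.5 the power sentence belongs to a test that the same section no longer plans, so giving it a new power value is somewhat beside the point. The Synopsis and Section 1.4 also call for descriptive reporting by arm, which leaves 9.4.1 as the only section that still plans the comparison. This is fair, and it makes deletion the main repair in 13.5. It does not help 9.4.1, which is current text and plans a test on counts that cannot be reached.

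The 15-versus-22 difference may be explicable: 9.4.1 counts patients with both biopsies, 13.5 counts samples, and archival tissue is not always available. The two effect sizes then follow from the two counts. This stands in part. However, the power sentence in 13.5 concerns the change, which needs pairs, and the plan does not explain the difference.

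The status of the endpoint also limits the harm. It is exploratory, no enrolment or efficacy decision depends on it, and combination treatment is already closed. Section 13.1.3 attaches the primary biomarker label to the ratio in each arm, while Section 2.4.1 attaches it to the change. The risk of misreading a null result is a possibility, not a certainty. All of this bears on severity and leaves the finding in place.

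Finally, the low end of the power range depends on assumed evaluability in Arm B. That is true, but the best case, with all 8 evaluable, is still 0.50–0.54 at 0.90 and 0.63–0.65 at 1.1.

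**Conclusion.** The concern holds. The claim of at least 80% power is true only for 22 versus 22 or 15 versus 15. With Arm B at 8 patients, power is about 40–65% for the sections' own pairings of Arm A count and effect size, depending on how many Arm B biopsies are evaluable. At an effect size of 0.90, no number of Arm A samples would restore 80%. Separately, 9.4.1 and 13.5 contradict each other on whether a between-group test is performed.

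The size of the shortfall rests on normal data, a standardized effect size and an assumed evaluable count in Arm B. That power falls below 80% is robust across the ranges examined. The primary efficacy analyses are not touched. The point should be corrected, but it does not threaten the trial's main conclusions.

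**What to change.** - **Section 9.4.1:** remove the between-group comparison, the 15-per-group estimate and the power statement. Refer to 13.5 for the analysis.
- **Section 13.5:** delete the power sentence. Replace the per-arm count with about 22 evaluable in Arm A and at most 8 in Arm B.
- **One stated analysis:** description by arm, in line with the Synopsis and Section 1.4. A within-patient change with a confidence interval in Arm A would be a useful addition, though it is not needed to remove the inconsistency.
- **If the comparison is kept:** label it exploratory and not fully randomized. Restate the power at 0.90 SD as about 42–54% for 6 to 8 evaluable Arm B patients, with the assumptions given.

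The cost is a wording amendment to two sections, with no new data, patients or procedures. The sponsor gives up a favourable power statement that the current design cannot support.

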### **14. PUBLICATION PLAN**

The results should be made public within 24 months of reaching the end of the study. The end of the study is the time point at which the last data items are to be reported, or after the outcome data are sufficiently mature for analysis, as defined in the section on Sample Size, Accrual Rate and Study Duration. If a report is planned to be published in a peer-reviewed journal, then that initial release may be an abstract that meets the requirements of the International Committee of Medical Journal Editors. A full report of the outcomes should be made public no later than three (3) years after the end of the study.

**APPENDIX A        PERFORMANCE STATUS CRITERIA**

ECOG Performance Status Scale		Karnofsky Performance Scale	
Grade	Descriptions	Percent	Description
0	Normal activity. Fully active, able to carry on all pre-disease performance without restriction.	100	Normal, no complaints, no evidence of disease.
		90	Able to carry on normal activity; minor signs or symptoms of disease.
1	Symptoms, but ambulatory. Restricted in physically strenuous activity, but ambulatory and able to carry out work of a light or sedentary nature (e.g., light housework, office work).	80	Normal activity with effort; some signs or symptoms of disease.
		70	Cares for self, unable to carry on normal activity or to do active work.
2	In bed <50% of the time. Ambulatory and capable of all self-care, but unable to carry out any work activities. Up and about more than 50% of waking hours.	60	Requires occasional assistance, but is able to care for most of his/her needs.
		50	Requires considerable assistance and frequent medical care.
3	In bed >50% of the time. Capable of only limited self-care, confined to bed or chair more than 50% of waking hours.	40	Disabled, requires special care and assistance.
		30	Severely disabled, hospitalization indicated. Death not imminent.
4	100% bedridden. Completely disabled. Cannot carry on any self-care. Totally confined to bed or chair.	20	Very sick, hospitalization indicated. Death not imminent.
		10	Moribund, fatal processes progressing rapidly.
5	Dead.	0	Dead.

## APPENDIX B        MULTI-CENTER GUIDELINES

### B-1. INTRODUCTION

The Dana-Farber/Harvard Cancer Center Multi-Center Data and Safety Monitoring Plan (DF/HCC DSMP) outlines the procedures for conducting a DF/HCC Multi-Center research protocol. The DF/HCC DSMP serves as a reference for any sites external to DF/HCC that are participating in a DF/HCC clinical trial.

#### B-1.1 Purpose

To establish standards that will ensure that a Dana-Farber/Harvard Cancer Center Multi-Center protocol will comply with Federal Regulations, Health Insurance Portability and Accountability Act (HIPAA) requirements and applicable DF/HCC Policies and Operations.

### B-2. GENERAL ROLES AND RESPONSIBILITIES

*For DF/HCC Multi-Center Protocols, the following general responsibilities apply, in addition to those outlined in DF/HCC Policies for Sponsor-Investigators:*

#### B-2.1 Coordinating Center

*The Coordinating Center is the entity that provides administrative support to the DF/HCC Sponsor in order that he/she may fulfill the responsibilities outlined in the protocol document and DSMP, and as specified in applicable regulatory guidelines (i.e. CTEP Multi-Center Guidelines).*

*The general responsibilities of the Coordinating Center may include but are not limited to:*

- *Assist in protocol development.*
- *Maintain FDA correspondence, as applicable.*
- *Review registration materials for eligibility and register participants from Participating Institutions in the DF/HCC clinical trial management system (CTMS).*
- *Distribute protocol and informed consent document updates to External Sites as needed.*
- *Oversee the data collection process from External Sites.*
- *Maintain documentation of Serious Adverse Event (SAE) reports and deviations/violation submitted by External Sites and provide to the DF/HCC Sponsor for timely review and submission to the IRB of record, as necessary.*
- *Distribute serious adverse events reported to the DF/HCC Sponsor that fall under the reporting requirements for the IRB of record to all External Sites.*
- *Provide External Sites with information regarding DF/HCC requirements that they will be expected to comply with.*
- *Carry out plan to monitor External Sites either by on-site or remote monitoring.*
- *Maintain Regulatory documents of all External Sites which includes but is not limited to the following: local IRB approvals/notifications from all External Sites,*

*confirmation of Federalwide Assurances (FWAs) for all sites, all SAE submissions, Screening Logs for all sites, IRB approved consents for all sites*

- *Conduct regular communications with all External Sites (conference calls, emails, etc) and maintain documentation all relevant communications.*

## B-2.2 External Site

*An External Site is an institution that is outside the DF/HCC and DF/PCC consortium that is collaborating with DF/HCC on a protocol where the sponsor is a DF/HCC investigator. The External Site acknowledges the DF/HCC Sponsor as having the ultimate authority and responsibility for the overall conduct of the study.*

*Each External Site is expected to comply with all applicable DF/HCC requirements stated within this Data and Safety Monitoring Plan and/or the protocol document.*

*The general responsibilities for each External Site may include but are not limited to:*

- *Document the delegation of research specific activities to study personnel.*
- *Commit to the accrual of participants to the protocol.*
- *Submit protocol and/or amendments to their IRB of record. For studies under a single IRB, the Coordinating Center will facilitate any study-wide submissions.*
- *Maintain regulatory files as per ICH GCP and federal requirements.*
- *Provide the Coordinating Center with regulatory documents or source documents as requested.*
- *Participate in protocol training prior to enrolling participants and throughout the trial as required.*
- *Update Coordinating Center with research staff changes on a timely basis.*
- *Register participants through the Coordinating Center prior to beginning research related activities when required by the sponsor.*
- *Submit Serious Adverse Event (SAE) reports to sponsor, Coordinating Center, and IRB of record as applicable, in accordance with DF/HCC requirements.*
- *Submit protocol deviations and violations to the Sponsor, Coordinating Center, and IRB of record as applicable..*
- *Order, store and dispense investigational agents and/or other protocol mandated drugs per federal guidelines and protocol requirements.*
- *Participate in any quality assurance activities and meet with monitors or auditors at the conclusion of a visit to review findings.*
- *Promptly provide follow-up and/or corrective action plans for any monitoring queries or audit findings.*
- *Notify the sponsor immediately of any regulatory authority inspection of this protocol at the External Site.*

## B-3. DF/HCC REQUIREMENTS FOR MULTI-CENTER PROTOCOLS

Certain DF/HCC Policy requirements apply to External Sites participating in DF/HCC research. The following section will clarify DF/HCC requirements and further detail the expectations for participating in a DF/HCC Multi-Center protocol.

### B-3.1 Protocol Revisions and Closures

The External Sites will receive notification of protocol revisions and closures from the Coordinating Center. When under a separate IRB, it is the individual External Site's responsibility to notify its IRB of these revisions.

- **Protocol revisions:** *External Sites will receive written notification of protocol revisions from the Coordinating Center. All protocol revisions should be IRB approved and implemented within a timely manner from receipt of the notification.*
- **Protocol closures and temporary holds:** *External Sites will receive notification of protocol closures and temporary holds from the Coordinating Center. Closures and holds will be effective immediately. In addition, the Coordinating Center, will update the External Sites on an ongoing basis about protocol accrual data so that they will be aware of imminent protocol closures.*

### B-3.2 Informed Consent Requirements

The DF/HCC approved informed consent document will serve as a template for the informed consent for External Sites. The External Site consent form must follow the consent template as closely as possible and should adhere to specifications outlined in the DF/HCC Guidance Document on Model Consent Language for Investigator-Sponsored Multi-Center Trials. This document will be provided separately to each External Site upon request.

External Sites must send their version of the informed consent document to the Coordinating Center for sponsor review and approval. If the HIPAA authorization is a separate document, please submit to the sponsor for the study record. Once sponsor approval is obtained, the External site may submit to their IRB of record, as applicable. In these cases, the approved consent form must also be submitted to the Coordinating Center after approval by the local IRB for all consent versions.

The Principal Investigator (PI) at each External Site will identify the appropriate members of the study team who will be obtaining consent and signing the consent form for protocols. External Sites must follow the DF/HCC requirement that for all interventional drug, biologic, or device research, only attending physicians may obtain initial informed consent and any re-consent that requires a full revised consent form.

